## PROTOCOL SYNOPSIS

Study Title	Enhancing Communication Between Children in EI and Their Depressed Mothers
Funder	North Carolina Translational and Clinical Sciences Institute, University of North Carolina at Chapel Hill
Clinical Phase	NA
Study Rationale	While maternal depressive symptoms can disrupt developmentally stimulating, child-centered speech, simple tools to assess and provide feedback to mothers can improve the child-centered speech and reciprocal language interactions that positively impact child outcomes. Although the LENA has been used in other studies and shown improvements in mothers' child-centered speech, the system has not been used with mothers showing depressive symptoms or in the EI context.
Study Objective(s)	Primary 

To test the feasibility and initial efficacy of embedding a language pedometer, the Language ENhancement Assessment/Intervention system (LENA) into Early Intervention (EI) to teach mothers to increase child-centered speech and reciprocal communication.

Test Article(s) (If Applicable)	Mothers who will run the Language Enhancement Assessment/intervention system with their young children, and will receive initial feedback from researchers on LENA output and how to enhance the language in the home language environment. The intervention involves mothers independently running the LENA system, an audio recorder language pedometer that records adult speech centered on the child, child vocalizations, and parent-child reciprocal turn-taking conversations. Researchers will provide an initial feedback session, which will include reviewing the LENA visual output from the previous recording and how mothers can access the output on their own for future recordings. Mothers will independently use the LENA system and access the output on their own.
Study Design	The investigators will examine the efficacy of using LENA in a pre-/post intervention design, where mothers will run the LENA for 1 day a week for a total of 6 weeks. Outcome measures will be collected prior to the first LENA recording and again after the final recording.
Subject Population	Inclusion Criteria 

Subjects age 18-99 years

key criteria for Inclusion and Exclusion:	
 
2. Biological or adoptive mother of an infant (6 weeks – 18 months old) or toddler (19-32 months old) enrolled in EI at the time of recruitment; mothers must be the primary caretaker of the child
 
3. Able to give consent independently, and must have adequate capacity to participate in the LENA intervention as well as understand what they will be asked to do as participants.
 
 
Exclusion Criteria
 
 
1. Currently pregnant by self-report
 
2. Child is completely deaf
 

Number Of Subjects	10
Study Duration	Each subject's participation will last approximately 2 months. The entire study is expected to last 12 months.
Study Phases Screening Study Treatment Follow-Up	(1) Screening : screening for eligibility, (2) Enrollment/Baseline : obtaining consent and conducting Time 1 outcome measures prior to intervention, (3) Intervention : study intervention using the LENA, and (4) Post-test/Analysis : Time 2 outcome measures after intervention and analysis
Efficacy Evaluations	Primary evaluation measure that will be used to assess the efficacy of the intervention is the LENA Adult Word Count.
Pharmacokinetic Evaluations	NA
Safety Evaluations	The MPIs will regularly monitor the study and data collection procedures and meet with the EI staff to review the protocols for safety and confidentiality. Drs. [name] and [name] will constantly monitor mothers whose depressive symptoms worsen and will arrange for immediate assessment if needed.
Statistical And Analytic Plan	Due to the small sample size and the feasibility/exploratory nature of the research questions, analyses will be descriptive only (means, standard deviations and/or frequencies).
DATA AND SAFETY MONITORING PLAN	The safety plan is described above. For management of data quality, [name] will work with [name], [name], and staff keying data to ensure data management activities (initial data cleaning, double keying, error checking and error corrections, and data validation) are conducted.

# 1 BACKGROUND AND RATIONALE

## 1.1 Introduction

Early Intervention (EI) services are provided to infants and toddlers with documented developmental delays in all 50 states and US territories. EI improves long-term infant-toddler adaptation and lowers the cost of care if parents use the services. However, depressive symptoms can reduce mothers' ability to provide the daily child development-promoting activities recommended by EI, increasing the child's risk for communication and behavioral problems. Indeed, repeated studies have shown that depressive symptoms reduce mothers' consistent use of developmentally sensitive, child-centered speech which, in turn, leads to negative child cognitive and behavioral outcomes.

## 1.2 Name and Description of Investigational Product or Intervention

*The Language Enhancement Analysis (LENA; [www.lenafoundation.org](http://www.lenafoundation.org)) system uses a non-invasive wearable sensor that (i) records language input and output, and (ii) provides visual feedback. When paired with simple tips for improving verbal input, it increases the quantity and quality of adult-child verbal interactions (Suskind et al., 2013). LENA is a validated tool for assessing adult and child speech and reciprocal interactions (Xu et al., 2009). The LENA system quantifies the number of words a child is exposed to, and the number of conversational turns between a child and adults over a 16-hour period (Gilkerson & Richardson, 2008). The LENA uses a shirt, vest or infant one-piece garment with an integrated audiotape device that records adult speech centered on the child, child vocalizations, and reciprocal turn-taking conversations between parent and child. Environmental noise (e.g., TV, non-caretaker speech) also can be recorded and analyzed in segments by LENA software. The quantified "language environment" is presented in a series of graphs which can be shown to parents to assist with goal setting. A "biofeedback" intervention model combines the visual data provided by LENA with customized "talking tips" for increasing adult word count and conversational turn taking (<http://www.providencetalks.org/wp-content/uploads/2015/09/Binder1.pdf>), which in turn results in improved reciprocal communication.*

## 1.3 Non-Clinical and Clinical Study Findings

This LENA intervention model showed success in increasing adult language production in parents of typically developing children (Suskind et al., 2013). In addition, LENA has been used successfully to document exposure to adult language in parent-child dyads in low-income families (Weisleder & Fernald, 2013), children with hearing loss (Caskey & Vohr, 2013), newborns in NICUs (Caskey et al., 2014), and in children with autism (Irvin et al., 2013; Yoder et al., 2013), and Down syndrome (Thiemann-Bourque et al., 2014). However, none of these studies explicitly explored the language environments of children with disabilities and mothers with depression, or "dually vulnerable" dyads, and no studies have addressed the use of LENA as an embedded tool within existing EI systems.

There are no known or expected risks to using the LENA system.

## 1.4 Relevant Literature and Data

Previous research showed that over one-third of mothers of children with disabilities have significant levels of depressive symptoms, a rate higher than the population at large. Infants and toddlers of

depressed mothers have been shown to receive fewer intensive services and have been shown to interfere with uptake of EI services through impaired mother-child interactions. A preliminary study by the investigators found that over a third of mothers in a large North Carolina county had severe depressive symptoms and depression histories. Fortunately, investigators also found that when depressed mothers were provided with concrete, attainable skills for improving interactions with their child, the impact of depression on both mother and child was substantially reduced. Focusing on a depressed mother's child-centered speech and reciprocal communication also improves outcomes, even when the child is cognitively compromised. However, none of these specialized services are part of EI best practices. Thus, EI is an ideal setting in which to integrate screening, referral, and targeted skills for depressed mothers in order to improve parent-child interactions and ultimately, child outcomes.

For the measures used to evaluate the efficacy of the LENA intervention, all have established reliability and validity: LENA adult word count, turn-taking, and child vocalizations (Xu, 2009); Parenting Sense of Competence (PSOC: Gilmore & Cuskelly, 2008); Patient Health Questionnaire – 9 (PHQ-9: Kronenke et al., 2001); Generalized Anxiety Disorder – 7 items (GAD-7: Spitzer et al., 2006).

## 2. STUDY OBJECTIVE

This project seeks to test the efficacy of this type of maternal-child focused intervention, using the LENA intervention embedded in EI to help mothers enhance their child-centered speech and reciprocal communication.

### 2.1 Primary Objective

The primary objective of the study is to test the feasibility and initial efficacy of embedding a language pedometer, the Language ENhancement Assessment/Intervention system (LENA) into Early Intervention (EI) to teach mothers to increase child-centered speech and reciprocal communication.

### 2.2 Secondary Objective - NA

## 3. INVESTIGATIONAL PLAN (brief overview)

### 3.1 Study Design

Type of design: Single group assignment, pre-/post-intervention

Provide brief overview of the study phases:

- Screening: screening for eligibility
- Enrollment/Baseline: obtaining consent and conducting Time 1 outcome measures prior to intervention
- Intervention: study intervention using the LENA
- Post-test/Analysis: Time 2 outcome measures after intervention and analysis

### 3.2 Allocation to Treatment Groups and Blinding (if applicable): NA

**3.3 Study Duration, Enrollment and Number of Subjects** 10 subjects will participate in the study. Each subject's participation will last approximately 2 months. The entire study is expected to last 12 months.

### **3.4 Study Population**

#### Inclusion Criteria

- Subjects age 18-99 years
- Biological or adoptive mother of an infant (6 weeks – 18 months old) or toddler (19-32 months old) enrolled in EI at the time of recruitment; mothers must be the primary caretaker of the child
- Able to give consent independently, and must have adequate capacity to participate in the LENA intervention as well as understand what they will be asked to do as participants.

#### Exclusion Criteria

- Currently pregnant by self-report
- Child is completely deaf

## **4. STUDY PROCEDURES (what will be done)**

### **4.1 Screening procedures**

Interest letters describing the study will be mailed from our Part C research partner to mothers in April -June 2018. Interested mothers will contact the research team by phone or email to schedule a time to screen them for eligibility for the study. Screenings will be done via phone by a research team member who will administer the PHQ-9 and collect demographic information.

### **4.2 Enrollment/Baseline Visit procedures**

For eligible mothers, researchers will schedule a home visit to go over enrollment procedures (i.e., complete consent forms). Enrolled mothers and their child who was the target for the study will complete the pre-test (Time 1) measures: the PHQ-9, the Parenting Sense of Competence, and the GAD-7. At this visit, mothers will be given written instructions and a video tutorial on how use the LENA system. The research team will leave the LENA recorder, clothing, and pre-stamped/addressed envelopes for the mother to mail the LENA recorder to the study team after the first recording was completed.

### **4.3 Intervention/Treatment procedures (by visits)**

Mothers will run the Language Enhancement Assessment/intervention system with their young child for the first time for one day up to 16 hours and will mail the recorder back to the research team. Researchers will provide an initial feedback session, which will include reviewing the LENA visual output from the previous recording and how mothers can access the output on their own for future recordings. Mothers will independently use the LENA system and access the output on their own for 5 additional recordings over 5 weeks, again mailing each recorder back to the team after the receiving it again from the research team once the recording is uploaded to the LENA system.

#### **4.4 Post-test/Analysis procedures (by visits)**

Once the final recording is returned, researchers will schedule a home visit to complete the post-test (Time 2) measures: the PHQ-9, the Parenting Sense of Competence, and the GAD-7.

Researchers will conduct descriptive analyses including means, standard deviation and/or frequencies.

#### **4.5 Unscheduled visits NA**

#### **4.6 Concomitant Medication documentation NA**

#### **4.7 Rescue medication administration (if applicable) NA**

#### **4.8 Subject Completion/ Withdrawal procedures**

Once recordings were completed an exit interview was conducted. Upon completion of this interview incentives were mailed to participants and subject participation was considered complete.

#### **4.9 Screen failure procedures**

We did not have any screen failures.

## **5. STUDY EVALUATIONS AND MEASUREMENTS (how measurements will be made)**

### **5.1 Efficacy Evaluation (if applicable)**

The following measures will be used to evaluate feasibility and efficacy of the LENA intervention; LENA data will be derived from the LENA audio recording. All other measures are collected using maternal self-report.

Primary:

- Change in LENA Adult Word Count after 6 weeks: The LENA system, which records adult-child vocalizations, measures the number of the target adult's (e.g., parent's) child-directed words (child-directed speech). The total possible range is 0-n, where higher scores indicate an increased number of child-directed words spoken by the target adult and higher degrees of a language-rich environment. Lower scores indicate fewer words spoken by the target adult and represent an environment that is not language-rich.

Secondary:

- Change in Parenting Sense of Competence Scale after 6 weeks: The Parenting Sense of Competence Scale is a 17-item measure assessing parental competence. Each item is rated on a 6-point Likert scale anchored by 1=Strongly Disagree and 6=Strongly Agree. The Efficacy subscale measures feelings of efficacy as a parent. It has 7 questions (1, 6, 7, 10, 11, 13, 15), producing a range of 6-42. Higher scores indicate greater self-efficacy. Lower scores mean more impairment.

- Change in the Patient Health Questionnaire – 9 after 6 weeks: The PHQ-9 is a depression scale used to assess brief depression severity by rating symptoms and functional impairment experienced in the last two weeks. The questionnaire contains a total of 9 questions, and each question is scored on a range from 0-3. The minimum value "0" represents not at all, "1" several days, "2" indicates more than half the days, and the maximum value "3" stands for nearly every day. The total possible range is 0-27, with higher scores indicating more depressive symptoms. The total number of each 0, 1, 2, 3 is added and multiplied by its value (0=0, 1=1, etc.) to produce a total score generated from the subtotal sum. The PHQ-9 total score is interpreted as follows: 0-4 represents minimal depression, 5-9 as mild depression, 10-14 as moderate depression, 15-19 moderately severe depression, and 20-27 severe depression.
- Change in LENA Mother/Child Turn Taking after 6 weeks: The LENA system, which records adult-child vocalizations, measures the number of conversational turns between the target adult (e.g., parent) and child. The total possible range is 0-n, where higher scores indicate and increased number of turns (back-and-forth, or "reciprocal" language exchanges) between the adult and child, reflecting higher degrees of a language-rich environment. Lower scores indicate fewer conversational turns between the adult and child, and represent an environment that is not language-rich.
- Change in LENA Child Vocalization after 6 weeks: The LENA system, which records adult-child vocalizations, measures the number of vocalizations of the target child. The total possible range is 0-n, where higher scores indicate an increased number of vocalizations from the child, reflecting higher levels of language development. Lower scores indicate fewer vocalizations from the child, and represent lower levels of language development.
- Change in GAD-7 after 6 weeks: The Generalized Anxiety Disorder 7-item (GAD-7) is a self-report screening of anxiety symptoms examining frequency of the specific behaviors within the last two weeks (e.g., not at all - nearly every day). A total score is calculated and compared to pre-determined cutoffs to help guide professionals in next steps for evaluation and treatment.

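### Do the misprinted 6-42 range and the loose outcome title leave the Parenting Sense of Competence score undefined?

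*Combined protocol and SAP*

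**What the plan says.** Among the secondary measures in Section 5.1 is "Change in Parenting Sense of Competence Scale after 6 weeks". The entry introduces the instrument, "The Parenting Sense of Competence Scale is a 17-item measure assessing parental competence", and gives the item scoring: "Each item is rated on a 6-point Likert scale anchored by 1=Strongly Disagree and 6=Strongly Agree". It then turns to one subscale, "The Efficacy subscale measures feelings of efficacy as a parent", and specifies it: "It has 7 questions (1, 6, 7, 10, 11, 13, 15), producing a range of 6-42". The direction follows: "Higher scores indicate greater self-efficacy". The entry gives no items, range or direction for any other PSOC score.

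Elsewhere the instrument appears by name only. Section 4.2 lists it among the Time 1 measures, and Section 4.4 does the same for Time 2: "researchers will schedule a home visit to complete the post-test (Time 2) measures: the PHQ-9, the Parenting Sense of Competence, and the GAD-7". Sections 6 and 6.3 plan descriptive summaries only, say that the sample is too small to test pre/post change, and name no PSOC score.

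**The concern.** Two things look wrong in the same entry. First, the printed range cannot be right: with a lowest item score of 1, seven answered items cannot sum to 6. An impossible limit in an outcome definition raises the question whether the item count, the anchors or the scoring rule is also wrong, and whether a form with a skipped item counted as zero might be accepted as valid.

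Second, the outcome title refers to the 17-item scale while the scoring refers to a 7-item subscale. A 17-item total and a 7-item sum lie on different scales. If the choice were truly open, a reader could not interpret the reported mean, and the score could be chosen after the data were seen. In a study that reports only descriptive summaries, the mean and SD are the whole result for this outcome, so it matters which score they describe.

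**Working it through.** **Inputs, all from Section 5.1.** Efficacy subscale: seven item numbers listed (1, 6, 7, 10, 11, 13, 15). Item scores: 1 to 6. Stated subscale range: 6-42. Full scale: 17 items.

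**Can the stated range be reproduced?** For a simple sum, minimum = items × lowest item score and maximum = items × highest item score.

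- Seven items scored 1-6: 7 × 1 = 7 and 7 × 6 = 42. The maximum reproduces; the minimum does not.
- Seven items scored 0-6: 0-42.
- Six items scored 1-6: 6-36.
- Six items scored 1-7: 6-42. Of the variants tried this is the only match, and it contradicts both the seven listed items and the stated anchors.

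The item list, the stated item count, the anchors and the upper limit all agree with one another. The 6 is the only figure out of line, by 7 − 6 = 1 point. That is the pattern of a slip in one digit, not of a different scoring rule.

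**Does the slip affect a result?** A mean, an SD and a change score are computed from the item responses; the printed limits do not enter. The sample size (Section 6.4) and the planned analysis (Section 6.3) do not use the PSOC range either.

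**Does it weaken data checking?** Section 10 promises cleaning, double entry, error correction and validation, but names no numerical limits and does not refer to Section 5.1. Suppose all the same that the printed range were used as a check. With one item skipped and scored zero, the sum runs from 6 × 1 + 0 = 6 to 6 × 6 + 0 = 36. A floor of 6 and a floor of 7 treat such a form differently only when the sum is exactly 6, that is, when all six answered items are 1. Sums from 7 to 36 pass either floor. Correcting the limit would therefore do almost nothing for skipped items; a rule on item completeness would be needed, and that is a separate matter from the range.

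**Which score does the text define?** Set the two candidates side by side:

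| | Efficacy subscale | 17-item total |
|---|---|---|
| Items listed | yes, seven | no |
| Range given | yes (minimum misprinted) | no |
| Direction given | yes, in terms of self-efficacy | no |
| Range on the stated anchors | 7-42 | 17 × 1 = 17 to 17 × 6 = 102 |

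The entry moves from instrument to score, range and direction, as the PHQ-9 entry does. On that pattern the Efficacy subscale is the score being defined. Sections 4.2 and 4.4 list which questionnaires are administered; naming the questionnaire there does not point to a total score.

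The widths of the two ranges are 42 − 7 = 35 and 102 − 17 = 85, a ratio of 85/35 = 2.43. This compares the greatest possible spreads. It does not say how far an observed change in the total would differ from one in the subscale, which depends on ten further items about which the documents say nothing.

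**The case for a change.** The strongest case for a change is that both points are real and can be mended in one line. No sentence says that the Efficacy subscale is the outcome, and the title says something broader. If the 17-item total were reported against the printed range, 60 of its 86 possible values (43 to 102) would lie above the stated maximum. With no test or model in the plan, a descriptive mean on an unnamed score is hard to read, and an open choice between total and subscale leaves room for selection.

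The arithmetic error stands, and so does the observation that the title is looser than the scoring beneath it. The rest carries less weight. The comparison of totals with 6-42 requires applying to the total a range that the text attaches expressly to the subscale. The room for selection is small, because only one score has been given a definition; reporting the total instead would mean supplying a scoring rule that the plan does not contain. The outcome is one of five secondary measures, and no conclusion of the study depends on it.

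**Conclusion.** No change to the plan follows. The lower limit of 6 should read 7; this is a clerical slip of one point that alters no computed quantity. The gap between title and scoring is missing detail that the surrounding text fills: an analyst would sum the seven listed items, score them so that higher means greater self-efficacy, and report the mean and SD at each time and for the change.

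This rests on two assumptions. One is that the sponsor scores the subscale the entry describes, which is the only reading for which the documents give a rule. The other is that the analysis stays descriptive, as Sections 6 and 6.3 state for 8 mothers (Sections 3.3 and 6.4 give 10), so that no decision depends on the limits of the score. If the 17-item total were meant, the entry would lack its scoring rule and range and the point would weigh more; nothing in the text suggests that this is so.
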